## Assessments

At the first prenatal visit all participants will complete an assessment addressing six areas: (1) Sociodemographics: age, yrs of education, race/ethnicity, marital status, and health insurance status. (2) Medical/pregnancy history: height/weight, self-reported pre-pregnancy weight, weeks pregnant, history of complications in prior pregnancies; unstable medical problems (e.g., preeclampsia) in current pregnancy; and use of medications, alcohol, and caffeine. (3) Smoking history: age started smoking, average number of cigarettes smoked per day now and immediately before this pregnancy, time to first cigarette in the morning, number of previous quit attempts, number of other smokers in the household, nicotine dependence/tolerance (Fagerstrom & Schneider, 1989), and nicotine withdrawal (Hughes & Hatsukami, 1986). Smoking Timeline Follow-back interviews will be conducted (Brown et al., 1998) to characterize daily smoking rates since learning of the current pregnancy. (4) Smoking attitudes: motivation to stop, confidence in ability to stop, intention to quit before the baby is born, intention to remain abstinent after the baby is born, and measures of perceived stress. (5) Biochemical verification of smoking status: breath CO and urine cotinine levels. (6) Mental health/executive function: lifetime history of depression, general psychiatric symptoms (Brief Symptom Inventory, Derogatis, 1993), current depressive symptoms (BDI, Beck & Beck, 1972), discounting of delayed

hypothetical monetary rewards (Johnson & Bickel, 2002). Appropriately modified versions of this battery will be completed again at the second prenatal care visit and 28-weeks gestation, and then 2-, 4-, 8-, 12-, 24-, and 48-weeks postpartum. We will also assess breastfeeding, including initiation, duration, and different levels of breastfeeding (e.g., exclusive, predominate, any). All women will complete the Postpartum Bonding Questionnaire to examine associations between breastfeeding and maternal/infant bonding (Brockington et al., 2001). Breastfeeding is associated with significant improvements in a wide range of maternal and infant health outcomes, but there have been few opportunities to examine experimentally altered rates of breastfeeding due to the absence of ethical methods to manipulate them (Ip et al., 2007). The proposed study may provide an opportunity to do so by altering smoking status, which in turn impacts breastfeeding duration (Higgins et al., 2010b). These assessments will be conducted with all subjects independent of smoking status or treatment condition. Women will receive \$50 per assessment independent of smoking status. We also plan to assess health outcomes and health care utilization for use in the cost-effectiveness analysis. Permission will be requested of all women to review maternal and infant health care records through one-year postpartum and to telephone mothers monthly during postpartum to review infant health and health care visits. Project staff will review records by obtaining faxed copies or visiting the offices of local providers/pharmacies at the time of each of the regularly scheduled assessments. We will track the incidence of smoking-related pregnancy complications, delivery complications, and maternal and infant health outcomes during the 1st year postpartum (all illnesses requiring a visit to a healthcare professional). Infant outcomes will include birth outcomes (mean birth weight, % low birth weight deliveries (< 2500 g), mean gestational length, % premature deliveries (< 37 weeks), incidence of NICU admissions and mean length of stay, and health outcomes through one year postpartum (respiratory distress syndrome, upper and lower respiratory infections, otitis media, sudden infant death syndrome, and other infant death). We will track all maternal prenatal and postpartum health care utilization including pharmacy use through one-year postpartum and infant utilization through one-

year postnatal. Greater than 99% of women in our trials deliver at our university teaching hospital and with maternal permission we will have access to all delivery and infant care records related to the delivery. Over the past 10 years 100% of women in our trials have provided permission to review maternal and infant medical records. We have used this system to obtain the birth outcomes data described above and will now extend that timeframe through the 1st year postpartum. We did not anticipate reviewing medical billings in our earlier studies and thus did not request permission. However, we anticipate no difficulty obtaining consent to review the cost data. Our staff has strong working relationships with local primary care clinicians, which will facilitate the logistics of our staff coordinating with them to review records.

### **Biochemical Verification of Abstinence**

Breath and urine specimens will be collected at each clinic visit. Breath CO levels will be analyzed using a breath CO Monitor. Readings < 6 ppm will indicate abstinence during week 1. Beginning in week 2, abstinence will be verified using onsite urine cotinine (< 80 ng/ml) analyzed with an Enzyme Multiplied Immunoassay Test (EMIT). Smoking-status classifications based on EMIT urine-cotinine levels using a cutoff of < 80 ng/ml are in > 98% agreement with those made by gas chromatography mass spectroscopy using a cut-point of 12.5 or 25 ng/ml (Higgins et al., 2007b). Urine and breath specimens will be collected at each of the follow-up assessments and analyzed similarly. Specimens collected at the end-of-pregnancy, and 12 & 24-week postpartum assessments will be sent to an outside laboratory for confirmation testing.

### **Monitoring Fetal/Infant Health**

**Fetal Growth.** We will compare the growth profiles for each of the fetal parameters measured across study conditions. This includes abdominal circumference, head circumference, femur length, estimated fetal weight and mid-thigh lean body and fat areas. We will also characterize birth weight between conditions employing birth weight percentiles (Bernstein et al., 1994; 1996; Fry, 2002). We have developed ultrasound techniques that are capable of distinguishing and quantifying specific fetal body

compartments with focus on the lean body and fat mass compartments (Bernstein et al., 1991; 1997; 2000). We will use this ultrasound technology to examine participants at 30 and 34 weeks of pregnancy to estimate changes in overall fetal growth and body composition. We will estimate fetal weight according to the method of Hadlock et al (1985) employing head circumference, femur length and abdominal circumference. We will estimate fetal peripheral muscle and fat areas according to the methods we have developed (Bernstein et al., 1991; 1997; 2000) and are now used broadly (Galan, 2001; Padoan, 2004; Larciprete et al., 2003). **Infant Growth.** Infant growth measures will also be obtained at 6 and 12 months. Weight will be obtained through the use of an electronic scale and length measurements will employ a measuring board that employs the tonic neck reflex for accurate assessment of infant length, thereby estimating ponderal index (Rohrer 1921, Walther & Ramaekers, 1982). At 6 and 12 months we will also measure skinfold thickness at 5 sites (triceps, subscapular, flank, anterior thigh and abdominal wall) (Bernstein 1991, 1997) to estimate subcutaneous fat stores. At 12 months only we will conduct an assessment of infant body composition using whole body dual x-ray absorptiometry (DEXA).

## Statistical Methods

Study conditions will be compared on baseline demographics and other characteristics using analysis of variance for continuous variables and chi-square tests for categorical variables. If a specific characteristic differs significantly across study conditions and is predictive of outcome, it will be considered as a potential covariate in subsequent analyses. Analyses of treatment effects on smoking status will be limited to smokers randomized to the two treatment conditions. We will adhere to an intent-to-treat approach (Armitage, 1983) wherein all women randomized to the study conditions will be included in the analyses independent of early dropout, noncompliance, etc., with the exception of excluding women for abortion/fetal demise as is convention in this research area. Cochran Mantel Haenszel tests (CMH) will be performed for comparisons of the two treatment conditions on point-prevalence smoking abstinence at end-of-pregnancy and 6-months postpartum assessments with

referring clinic as a stratification variable. The Breslow-Day Test will be used to examine the homogeneity of treatment effects across referring clinics. Comparisons of point-prevalence abstinence rates between treatment conditions across all assessments through one-year postpartum will be analyzed using mixed model repeated measures for categorical data based on generalized estimating equations (GEE) utilizing a logistic link function (SAS: PROC GENMOD, SAS Institute, Cary, NC). We will include women from the nonsmoker condition in analyses of fetal growth, birth outcomes, and breastfeeding and other postpartum outcomes. Comparisons of treatment conditions on dichotomous outcomes (e.g. % low birth weight, % preterm, % NICU admissions, % breastfeeding, % medical treatment in first year) will parallel categorical analyses for point prevalence abstinence using PROC GENMOD to adjust for strata (referring clinics) and potential covariate effects. Analysis of covariance will be used to compare study conditions on mean birth weight adjusting for variables known to predict birth weight (i.e., maternal prepregnancy BMI, parity, and sex), mean gestational age at delivery, and frequency measures of medical illnesses. Statistical analyses of fetal growth outcomes (i.e. estimated fetal weight, fetal lean area, fat area, femur length and head circumference) will be based on linear growth models with slope and intercept as random effects (SAS PROC MIXED). This methodology allows for the within-subjects ultrasound assessments not to be at identical timepoints across subjects. Study condition will be considered a fixed factor with fetus nested within study condition. Two-way analyses of covariance will also be used for analyzing effects of study condition and referring clinic on DEXA body composition measures at 12 months. Additional subject level covariates will include maternal pre-pregnancy body mass index, maternal age and fetal gender. Analyses of infant growth will parallel those used to examine fetal growth. Repeated measures analyses of variance will be used to test for differences between study conditions in skinfold thickness obtained during infant 1st year of life and continuous measures of medical illnesses. Significance will be based on alpha = .05 for all analyses.

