being nonsmokers at the time they learned of the current pregnancy, report no smoking in the past 6 month, and report smoking < 100 cigarettes in their lifetime, the conventional definition of a never smoker (Pomerleau et al., 2004). Recruiting never smokers will substantially reduce the likelihood of women in this condition converting to smoker status during the study. They must also meet other study inclusion criteria listed above and will be frequency matched to women in the two smoker conditions on the following characteristics that may influence outcomes: (1) maternal education (% < 12 years), (2) pre-pregnancy body mass index (% > 25, % > 30), (3) parity (% primigravida), (4) age (% < 20 yrs), (5) comorbidities (% diabetic, % hypertensive), and (6) recreational use of cocaine/opioids in past 12 months (% reporting yes). Initially, the distributions of these characteristics will be based on our previous trials but where necessary adjustments will be made as smokers are enrolled into the proposed trial. Because women will be recruited at the start of their prenatal care, we will not yet know infant sex and thus will not be able to balance across conditions on that characteristic. We anticipate comparable distribution of infant sex across study conditions, but will include it as a covariate in analyses of birth and infant health outcomes if it differs significantly across study conditions.

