## Sample Size Justification

Sample size was determined to have sufficient power to detect differences between study conditions corresponding to our primary hypotheses regarding point prevalence smoking abstinence at late pregnancy and 24weekpostpartum assessments, fetal growth, birth weight, and breastfeeding. Estimates of abstinence were based on our prior trials where 7-day point-prevalence abstinence in the incentives vs. control conditions were 34% vs. 7% at the late-pregnancy assessment and 14% vs. 1% at 24weeks postpartum assessment, respectively (Higgins et al., 2010a). We estimated that the proposed increase in the value of the incentives used with heavier smokers will increase late-pregnancy abstinence rate to approximately 50% in the incentives condition while the best practices alone condition is estimated at <10%. Assuming a decline in abstinence of approximately 20% from late-pregnancy to the 24-week postpartum assessment as we saw in our prior trials, we estimate abstinence rates of approximately 30% vs. < 5% at 24weeks postpartum in the best practices plus incentives vs. best practices alone conditions, respectively. The proposed sample size of 115 per study condition will result in greater than 90% power to detect a difference between the two treatment conditions in abstinence rates of 50% vs. 10% at late-pregnancy or 30% vs. 5% at 24weeks postpartum assessments using a chi-square test. The proposed sample size is also expected to be more than sufficient for examining differences between study conditions in fetal growth, birth weight, and breastfeeding outcomes. The proposed sample size after considering noncompliance in completing scheduled ultrasounds is estimated to have power of 80% for detecting a mean growth difference of 23 g/wk in estimated fetal weight between any two conditions based on our estimated pooled within group SD=49.7. This difference is slightly more than half the difference observed between the incentive and control condition in our 2008 study (Heil et al, 2008) and represents a conservative expected difference. With respect to mean birth weight, power is estimated to be 80% to detect a difference of approximately 200 g between any two study conditions assuming a pooled SD=550, which aligns well with treatment effects in our study combining results across prior trials (Higgins et al., 2010a) where

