mean birth weights were  $3295.6 + 588$  g vs.  $3093.6 + 603$  g in the incentives and control conditions, respectively and with our estimate of a mean birth weight of  $3595.6 + 404$  g in the nonsmoker condition. For this estimate of the mean birth weight that might be expected in the nonsmoker condition, we examined birth weights in a sample ( $n = 88$ ) of women followed in our clinic who were smokers at the time that they learned of the current pregnancy but quit prior to entering prenatal care (i.e., spontaneous quitters) and were continuously abstinent through the remainder of antepartum. We are estimating breastfeeding rates of 50% and 30% in the incentives condition and 17% and 13% in the best practices alone condition at 12 and 24 weeks postpartum, based on our prior study results (Higgins et al., 2010b) and our planned use of higher value vouchers with heavier smokers in the proposed study. Again using the same group of spontaneous quitters but restricting it to women who remained abstinent through 24-weeks postpartum ( $n=32$ ), the estimated percent breastfeeding at 12- and 24-weeks postpartum was 70% and 48%. Using chi-square tests, we will have over 80% power to detect differences in rates between any two of the three study conditions at the two assessments. Power calculations were done using a two-sided significance level of .05.

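### The birth-weight ANCOVA includes the non-randomised nonsmokers and names no error term for incentives vs best practices; with the usual pooled error the type I error is about 7.6% if the 404 g proxy SD holds, and 5% if SDs are equal

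*Combined protocol and SAP*

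**What the plan says.** Under Statistical Methods, one group of analyses is confined to the randomised women: "Analyses of treatment effects on smoking status will be limited to smokers randomized to the two treatment conditions". No such limit is set for birth outcomes. The same section says the opposite about the third condition: "We will include women from the nonsmoker condition in analyses of fetal growth, birth outcomes, and breastfeeding and other postpartum outcomes". It then gives the model: "Analysis of covariance will be used to compare study conditions on mean birth weight", with pre-pregnancy BMI, parity and sex as covariates. It names no pairwise contrast, no error term, no allowance for unequal variances and no separate two-arm analysis of birth weight. The section closes with "Significance will be based on alpha = .05 for all analyses". None of the entries under History of Modifications changes the analysis of mean birth weight.

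Sample Size Justification lists birth weight among the outcomes of the primary hypotheses. It plans for 80% power at about 200 g "between any two study conditions assuming a pooled SD=550". It also reports birth-weight SDs of 588 g (incentives) and 603 g (control) from prior trials, and 404 g for the expected nonsmoker condition. The 404 g comes from 88 women who had been smokers but who "quit prior to entering prenatal care (i.e., spontaneous quitters) and were continuously abstinent through the remainder of antepartum".

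The women actually enrolled in the third condition are different. Under Participants they must "report smoking < 100 cigarettes in their lifetime, the conventional definition of a never smoker", and they are "frequency matched to women in the two smoker conditions on the following characteristics that may influence outcomes".

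**The concern.** Only the 230 smokers are randomised. If the incentives vs best-practices difference is read from a three-condition ANCOVA with a single residual variance, the nonsmokers supply about a third of the information on the error variance of a contrast they are not part of. When the three conditions vary equally, this does no harm and adds degrees of freedom. When nonsmokers vary less, the standard error of the randomised contrast is too small, its confidence interval too narrow and its test too liberal. When they vary more, the test is conservative.

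The only SDs in the documents point to the liberal case. The stated .05 level for this randomised comparison would then depend on the spread of a non-randomised group. An unstated error term also leaves room to choose it after the data are seen. At these SDs, an unadjusted difference of 150 g would be significant with one error term and not with the other, because the 95% half-widths are 139.9 g and 154.8 g.

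**Working it through.** **Inputs.** From Sample Size Justification: 115 per condition; two-sided alpha .05; planning difference 200 g; planning SD 550 g; reported SDs 588, 603 and 404 g; n = 88 behind the 404 g.

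**1. The plan's own figure.** SE = 550 × √(2/115) = 72.5 g. Power for 200 g = Φ(200/72.5 − 1.96) = 78.7%. The difference detectable at 80% power is (1.96 + 0.84) × 72.5 ≈ 203 g. The stated 80% at about 200 g is therefore reproduced to within rounding.

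**2. The two candidate error terms, unadjusted.**
- Three conditions: √((588² + 603² + 404²)/3) = √(872,569/3) = 539.3 g; SE = 539.3 × √(2/115) = 71.1 g; 95% half-width 139.9 g (342 df).
- Two randomised arms: √((588² + 603²)/2) = √(709,353/2) = 595.5 g; SE = 595.5 × √(2/115) = 78.5 g; 95% half-width 154.8 g (228 df).
- Ratio 539.3/595.5 = 0.9056, so the pooled SE is about 9% too small.

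**3. Type I error.** The difference truly varies with the two-arm SE but is judged against the pooled SE. The actual size is therefore 2 × (1 − Φ(1.96 × 0.9056)) = 2 × (1 − Φ(1.775)) = 7.6%, and the nominal 95% interval covers 92.4%.

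**4. Dependence on the nonsmoker SD.** Simulated null rejection rates (2,000,000 trials per row, smoker arms at 588 and 603 g):

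| Nonsmoker SD (g) | Three-condition pooled error | Two-arm error |
|---|---|---|
| 352 (lower 95% limit of proxy) | 8.3% | 5.0% |
| 404 (proxy) | 7.6% | 5.0% |
| 474 (upper 95% limit of proxy) | 6.6% | 5.0% |
| 595.5 (equal spread) | 5.0% | 5.0% |
| 650 (assumed) | 4.3% | 5.0% |

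A model with separate variances and Satterthwaite degrees of freedom also gives 5.0% in every row. The limits are 404 × √(87/χ²) with 87 df, assuming normality. They cover sampling error of the proxy only, not whether it applies to never smokers.

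**5. Covariate adjustment.** With ρ the ratio of nonsmoker to smoker residual SD, size = 2 × (1 − Φ(1.96 × √((2 + ρ²)/3))). A ratio of 0.68 (404/595.5) gives 7.6%, 0.59 to 0.80 gives 8.3% to 6.6%, and 1.0 gives 5.0%. The documents give no residual SDs. If the covariates explain the same share of variance in each condition, 7.6% is unchanged. If they remove the same absolute variance (assumed 20,000 to 80,000 g²), it is about 7.7% to 8.5%.

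**6. Group sizes.** At SDs 588/603/404, equal sizes of 95, 100 or 105 leave 7.6%. Sizes of 100/100/115 (incentives, best practices, nonsmokers) give 8.0%, and 115/115/88 gives 7.0%.

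**7. Power for 200 g at the same SDs, unadjusted, by simulation.** 77.8% nominal with the pooled error, 71.8% with the two-arm error. With the latter, 80% power needs about 221 g.

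**The case against.** The strongest reply is that the plan is silent rather than wrong. The 7.6% needs three things together: the randomised contrast is taken from the three-condition ANCOVA, that model has one residual variance, and 404 g describes never smokers. The plan states none of these for this contrast. Its use of the term for study conditions is also loose, since the intent-to-treat sentence applies it to the randomised arms only. This stands in part, and the finding is conditional for that reason. But the sentence bringing nonsmokers into the birth-outcome analyses makes the three-condition model the likely reading, and a single residual variance is what ordinary ANCOVA uses.

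Secondly, the 88 quitters were brought in to estimate a mean; the planning SD is 550 g. Read as a common SD, 550 g implies no inflation. But 550 g is below both smoker SDs, so unadjusted pooling of those two arms cannot produce it. If it is a three-condition pooled value with the smoker arms at 588 and 603 g, the nonsmoker SD is √(3 × 550² − 588² − 603²) ≈ 445 g and the size about 7.0%. Rounding or an allowance for covariates could also explain 550 g.

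Thirdly, the proxy was selected on quitting and sustained abstinence, whereas the actual group is matched never smokers whose spread might be closer to that of the smokers. That stands. At a nonsmoker SD of 500 to 550 g the size is 6.2% to 5.6%.

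Finally, the reach is limited. Economic Evaluation calls antepartum abstinence primary, and the abstinence analyses are already confined to randomised smokers. The choice of error term does not itself bias the estimated birth-weight difference. That too stands, and it bounds the importance of the point.

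**Conclusion.** The concern holds. As written, the plan leaves open the error term for a randomised comparison listed among its primary hypotheses. The ordinary reading of the stated model gives a miscalibrated test at the only SDs the documents report: type I error about 7.6% in place of 5%, with 92.4% interval coverage.

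That figure rests on prior-trial SDs of 588 and 603 g for the smoker arms, a 404 g proxy for the nonsmokers, one residual variance, about equal group sizes, and either no covariate adjustment or adjustment that leaves the SD ratio unchanged. Within the proxy's sampling error it is 6.6-8.3%. With equal SDs there is no inflation, and with more variable nonsmokers the test is slightly conservative. The SD of never smokers is not given, so the size in the actual trial cannot be fixed from the documents. No inflation is shown for other outcomes. The plan should be changed on this point, with medium confidence in the size of the effect.

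**What to change.** State in Statistical Methods that the incentives vs best-practices difference in mean birth weight will be estimated in one of two ways:

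- ANCOVA with the same covariates in the two randomised arms only; or
- the three-condition model with condition-specific residual variances (PROC MIXED, REPEATED / GROUP=condition) and Satterthwaite degrees of freedom.

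Choose one in advance, not according to the observed variances. Comparisons with nonsmokers stay in the three-condition model. The same rule could be applied to the other ANCOVA outcomes for consistency only.

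The cost is one sentence in the plan and one line of code. The nominal power for 200 g will look lower, about 72% in place of 78% unadjusted at these SDs. That gap reflects the understated standard error; no information is lost.

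### Referring clinic is adjusted for in the abstinence, dichotomous and DEXA analyses, but no clinic term is named for mean birth weight, gestational age, fetal growth, infant growth or skinfolds, which leaves the never-smoker contrasts open to clinic mix

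*Combined protocol and SAP*

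**What the plan says.** All of this is in Statistical Methods unless another section is named.

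**Where clinic enters.** The Cochran-Mantel-Haenszel tests of abstinence take "referring clinic as a stratification variable", and a Breslow-Day test looks at homogeneity across clinics. The dichotomous birth and postpartum outcomes are analysed "using PROC GENMOD to adjust for strata (referring clinics) and potential covariate effects". The two-way analysis of covariance for body composition examines "effects of study condition and referring clinic on DEXA body composition measures at 12 months".

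**Where it does not.** The analysis of covariance sentence covers "mean birth weight adjusting for variables known to predict birth weight (i.e., maternal prepregnancy BMI, parity, and sex", and goes on to "mean gestational age at delivery, and frequency measures of medical illnesses", with no mention of clinic. For the fetal growth models: "Study condition will be considered a fixed factor with fetus nested within study condition". Then: "Analyses of infant growth will parallel those used to examine fetal growth". Skinfold thickness gets a repeated measures analysis of variance, again without a clinic term.

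**Never smokers.** They are included in the fetal growth, birth and postpartum comparisons. The Participants section recruits them from the same clinics as the smokers and says they "will be frequency matched to women in the two smoker conditions on the following characteristics that may influence outcomes". The six characteristics are education, body mass index, parity, age, comorbidities and cocaine or opioid use. Clinic is not one of them.

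**General covariate rule.** A baseline characteristic that differs significantly between conditions and also predicts outcome becomes a candidate covariate. Clinic is not named there.

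**The concern.** The plan treats clinic as worth adjusting for in some outcomes and omits it, without a reason, for others measured on the same deliveries and infants. The cleanest pair is percent preterm (clinic-adjusted) and mean gestational age (not). Two summaries of the same outcome could then differ partly because their adjustment sets differ.

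What is at stake depends on the contrast. Randomisation protects the comparison of the two treatment arms, so only precision is involved. Never smokers are not randomised. Drawing them from the same clinics fixes which clinics contribute, but not in what proportions. If clinics differ in mean birth weight or growth, and never smokers are spread over them differently from smokers, part of the never-smoker difference is a clinic difference. Sample Size Justification lists fetal growth and birth weight among the primary hypotheses and states power for any two conditions. The Project Summary uses the never-smoker group to judge how much of the burden of smoking each treatment removes.

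**Working it through.** **Inputs from the documents.** 115 per condition; 200 g difference, SD 550 g, 80% power, two-sided 0.05; expected mean birth weights 3295.6 g (incentives), 3093.6 g (control) and 3595.6 g (nonsmokers, estimated from spontaneous quitters). The number of clinics and the size of clinic differences are not given.

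**1. The plan's own figure.** SE = 550 × √(2/115) = 72.5 g. Power = Φ(200/72.5 − 1.96) = 78.7% (78.4% by noncentral t). The difference detectable at 80% power is 203 g, so the plan's roughly 200 g at 80% reproduces from an unadjusted two-group comparison.

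**2. Expected never-smoker differences.** Against incentives, 3595.6 − 3295.6 = 300 g. Against control, 3595.6 − 3093.6 = 502 g.

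**3. Shift left in by not adjusting (assumed inputs).** With two groups of clinics, shift = (difference in clinic means) × (difference in clinic share).

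| Clinic mean difference | Mix differs by 10 points | 20 points | 30 points |
|---|---|---|---|
| 50 g | 5 g | 10 g | 15 g |
| 100 g | 10 g | 20 g | 30 g |
| 200 g | 20 g | 40 g | 60 g |

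The range of 5 to 60 g is 5/300 = 1.7% to 60/300 = 20% of the smaller expected difference, and 5/502 = 1.0% to 60/502 = 12% of the larger.

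**4. Effect on the burden estimate.** On the planning means, incentives remove 3295.6 − 3093.6 = 202 g of a 502 g gap, or 40%. If a shift of 60 g applied equally to both smoker arms, the share would read 202/562 = 36% or 202/442 = 46%, depending on direction. A shift of 5 g gives 202/507 = 39.8% or 202/497 = 40.6%.

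**5. Would the general covariate rule catch it?** Take 115 never smokers and 230 smokers, with assumed shares of one clinic group.

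- 50% versus 30%: pooled share 0.367; chi-square = [115 × 0.133² + 230 × 0.067²]/(0.367 × 0.633) ≈ 13 on 2 df, p ≈ 0.001. The first condition of the rule would probably be met.
- 40% versus 30%: pooled share 0.333; chi-square = [115 × 0.067² + 230 × 0.033²]/(0.333 × 0.667) ≈ 3.5 on 2 df, p ≈ 0.18. The rule would usually not fire, although 20 g could remain if clinics differ by 200 g.

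**6. Cost and gain of adding clinic.** Power for 200 g by noncentral t, three-group model, residual df = 345 − 3 − (k − 1), with k from 2 to 20 clinics balanced across conditions (assumed):

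- clinic explains no variance: 78.5% at every k, so the loss of df costs under 0.1 point;
- clinic explains 1%: 78.9%;
- clinic explains 5%: 80.5%;
- clinic explains 10%: 82.6%.

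**The case against.** The strongest reply is that the plan already has a safeguard in its general covariate rule, and that a large clinic imbalance would probably trigger it. This is partly right. The rule does not name clinic, depends on a significance test, misses moderate imbalance (step 5), and even when met only makes clinic a candidate. It is not a commitment.

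Second, the routes for clinic confounding are narrow. All women are Medicaid recipients from one area, matched on six characteristics, and the Assessments section reports that over 99% of women in the earlier trials delivered at one hospital. This stands as a reason to expect a small effect. It does not explain why clinic is kept for preterm birth and NICU admission and dropped for mean gestational age.

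Third, the text may be a summary and not a full model statement. The listed covariates could be only the known predictors of birth weight, and the DEXA sentence or the subject-level covariates after it might have been meant more widely. That is possible, but those further covariates are body mass index, maternal age and fetal gender. No reading puts clinic into these models explicitly.

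A reader might also infer four stronger claims that the documents do not support:

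- *The treatment effect on birth weight is biased.* It is not; the two arms are randomised.
- *The randomised standard errors are wrong because randomisation was stratified by clinic.* No section says that it was. Clinic is a stratum of the analysis. If randomisation had been stratified, and clinic explained 2% to 5% of variance, the unadjusted SE would be too wide by 1/√(1 − R²), that is 1.0% to 2.6%.
- *False positives are inflated in the never-smoker contrast.* Shifts of 5 to 60 g would move a nominal 5% to between 5.1% and 13.1%, but the plan expects differences of 300 to 502 g there, so error under a null of no difference is not the relevant measure.
- *The same birth weight is clinic-adjusted when dichotomised and not as a mean.* The January 2020 modification replaced low birth weight with small-for-gestational-age, which is not birth weight simply cut in two. The preterm and gestational-age pair is the sound example.

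**Conclusion.** The point holds as an inconsistency of adjustment with a modest consequence. Clinic is adjusted for in the abstinence, dichotomous and DEXA analyses and is not named for mean birth weight, gestational age, fetal growth, infant growth or skinfolds. For the randomised comparison the effect is at most a small loss of precision. For the never-smoker contrasts, clinic mix is neither matched nor adjusted by commitment.

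The size cannot be derived from the documents. The 5 to 60 g range rests on assumed clinic differences of 50 to 200 g and mix differences of 10 to 30 points. Nothing in that range would overturn differences of 300 to 502 g. It could move the estimated burden of smoking that remains after treatment by a few percent up to about a fifth. The case for change rests on that estimate, on consistent treatment of related outcomes and on precision. This is an inexpensive improvement and not a threat to the trial's main conclusion.

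**What to change.** Prespecify referring clinic as an additive fixed factor, without a clinic-by-condition term, in:

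- the analyses of covariance for mean birth weight and gestational age;
- the fetal-growth and infant-growth mixed models;
- the repeated measures analysis of variance for skinfolds.

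In the growth models a clinic main effect adjusts level only. Since the powered fetal contrast is a growth rate, say whether clinic also enters the slope. Fix any rule for pooling very small clinics before the analysis. If clinic is left out of any of these models on purpose, state the reason.

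The cost is wording in Statistical Methods and a few degrees of freedom (k − 1 for k clinics, out of 342 in a three-group model). Clinic must already be recorded for the abstinence and dichotomous analyses, so no new data are needed.
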